### 1.3 Secondary Study Endpoints

Not applicable.

## 2.0 Background

### 2.1 Scientific Background and Gaps

Neurological injury in the form of traction or crush to nerves that control muscles and sensory function is common. Because an understanding of these injuries is only now beginning to emerge, research on potential treatments is an important next step. Through experiments performed on animals with the Acorda Therapeutics, Inc. version of the drug (AMPYRA®), 4-aminopyridine (4-AP) has been strikingly effective in ameliorating the effect of a standardized peripheral nerve crush injury. The peripheral nerve injury used in our experiments was a standard model of peripheral nerve injury used to measure recovery in animals and is a model of peripheral nerve traction and crush injury that has been studied for over thirty years. We have found that:

- (1) 4-AP administration in a single dose given on day three after the injury led to a drastic reduction in the dysfunction afforded by a crush injury just days after the crush itself.
- (2) 4-AP treatment's effect was short-lived after a single dose and was, in effect, diagnostic of the potential to recover in a nerve that was crushed but not shattered.
- (3) Severed nerves show no capacity to recover even with 4-AP treatment.
- (4) The treatment in a daily regimen led to profound, lasting, permanent improvement in the speed of recovery in these animals.

4-AP is used in some of the most fragile of neurologically-ailing patients and is currently a mainline treatment in the setting of multiple sclerosis. Multiple sclerosis patients suffer a demyelinating disorder that causes the stripping of the myelin sheath from around neurons in the peripheral and central nervous system. The myelin covering allows for normal conduction of impulses and, without such covering, impulses are small, impaired, impeded, and ineffective. The recognition that crush injuries to nerves do not simply sever the axonal fibers but also demyelinate some population of nerve cells has led to the idea to study the treatment of peripheral nerve traumatic injuries in humans using 4-AP.

## 2.2 Previous Data

4-AP has been studied in humans since the early 1980s, and principles of safe usage are extremely well established. For the purposes of this proposal, the immediate release formulation of 4-AP, sometimes called fampridine will be referred to as IR 4-AP. The proposed version of the drug used in this study is an extended release formulation of 4-AP, called dalfampridine, which was marketed under the trade name AMPYRA, by Acorda Therapeutics. Recently, this extended release formulation has become available as a generic, which will be referred to as generic AMPYRA or dalfampridine. Essentially identical principles apply whether 4-AP is provided in an orally available immediate release formulation (IR 4-AP) or an orally available sustained release formulation (dalfampridine). The safety of 4-AP appears to be determined solely by serum levels.

It has long been recognized that the most significant safety concern regarding 4-AP is an increased frequency in seizures, which occurs in a small percentage of patients if serum levels exceed 100 ng/ml. Therefore, dosages are chosen to maintain serum levels that do not exceed 50-60ng/ml. In prior studies, 5mg of study drug were administered once every six hours, for a total dosage per day of 20 mg. This total dose, as indicated by multiple previous studies on immediate release 4-AP, has an excellent safety profile even in the fragile population of patients with multiple sclerosis. A sustained release formulation of 4-AP (AMPYRA®) at this same dose is FDA approved for use in the multiple sclerosis population even with a known risk of seizure activity in these patients.

It is important to note that multiple studies on 4-AP also include patients with chronic stroke, chronic spinal cord injury, transverse myelitis, primary lateral sclerosis, Lambert-Eaton myasthenic syndrome, ocular nystagmus, nonarteritic anterior ischemic optic neuropathy, spinal muscular atrophy, chronic Guillan-Barre syndrome, episodic ataxia Type 2, obstructive sleep apnea and spinocerebellar ataxias. Over 45 clinical trials have been conducted in the US alone (as listed on the Clinicaltrials.gov website). There are also 49 primary publications on clinical trials outcomes on 4-AP, which include patients with multiple sclerosis, chronic spinal cord injury, spinocerebellar ataxias and chronic stroke.

The many trials on 4-AP have been conducted using both immediate release 4-AP and sustained release 4-AP. The difference between the immediate release and sustained release formulations are that the sustained release formulation helps to decrease the peaks and troughs in serum levels that can occur with larger doses of immediate release formulations.

In respect to the use of *immediate release* formulations of 4AP (not proposed for use in this study but relevant for evaluation of safety), the following studies on multiple sclerosis patients are the most pertinent:

1. 4-Aminopyridine in patients with multiple sclerosis: dosage and serum level related to efficacy and safety. Van Diemen HA, Polman CH, Koetsier JC, Van Loenen AC, Nauta JJ, Bertelsmann FW. Clin Neuropharmacol. 1993 Jun;16(3):195-204.

In these studies, nonenteric-coated capsules containing 4-AP or placebo were administered orally for 12 weeks, the starting dosage was 10-20 mg orally per day in 2-3 divided doses. The daily dosage was elevated with 5-15 mg at week two and week six. Blood samples, to determine serum levels at the end of the first and second oral treatment, were taken 1.5-2.5 hours after the latest intake of medication.

Side effects were minimal in these studies and mostly were confined to paresthesias and/or dizziness/lightheadedness and nausea/vomiting and were not considered to be significant by the patients.

The mean dosage given to patients was 31.2 mg per day and ranged from 10-50 mg per day. Thus, the average dose was higher than we have proposed.

Capsules were divided in 2-4 doses and ranged from 0.17- 0.55 mg/ kg. On average, 4AP serum levels increased 1.3 ng/ml per mg 4- AP/day. Side effects were less frequent with oral dosing than with intravenous dosing. When side effects occurred, they mostly occurred within 30-45 minutes after taking the medication and generally resolved within 2-5 hours, with half the patients not experiencing any side effects.

The rapid resolution of side effects with orally administered 4-AP in an immediate release formulation was very favorable.

One patient, who received three oral doses daily at twice the concentration that are proposed (i.e., 10mg per capsule instead of 5 mg/capsule), was closely studied at multiple time intervals in this very early study. Following an initial rapid climb in serum levels to 114 ng/ml, subsequent doses caused increases to lower levels of 60 ng/mL or 80 ng/ml.

In general, restlessness, confusion and generalized tonic-clonic seizures have been reported at doses higher than 0.8 mg/kg bodyweight, and such symptoms were not seen when doses of 0.5 mg/kg bodyweight or less were used.

For this IND application, we are assuming a body weight of 70kg, the dosages proposed are <0.3 mg/kg, distributed in 1 dose of 10mg/capsule. No subject will receive a dose greater than 0.5 mg/kg bodyweight. Patients will receive only one pill for the course of the study.

2. The effect of 4-aminopyridine on clinical signs in multiple sclerosis: a randomized, placebo-controlled, double-blind, cross-over study. van Diemen HA, Polman CH, van Dongen TM, van Loenen AC, Nauta JJ, Taphoorn MJ, van Walbeek HK, Koetsier JC. Ann Neurol. 1992 Aug;32(2):123-30.

In this study, patients reported side effects (which were mild when they occurred at all) that occurred within 30-45 minutes after taking the medication, and generally resolved within 2 -5 hours. Severe side effects were not encountered which was thought to be due to the fact that the maximum daily dose was only 0.5 mg/kg of body weight.

3. 4-Aminopyridine improves clinical signs in multiple sclerosis. Stefoski, D., Davis, F.A., Faut, M., Schauf, C.L., 1987.. Ann Neurol 21, 71-77.

In these patients, single doses up to 15 mg 4-AP were administered in an immediate release oral formulation. In this single-dose administration, 70% of the improvements lasted 7 to 10 hours and usually became apparent one hour post-4-AP and culminated three hours or so later.

Serum samples were taken from a heparin lock placed in a peripheral arm vein before 4-AP initiation and at 0.5, 1.0, 1.5, 2, 3, 4, 6, and 8 hours after the dose. Analysis of serum concentrations of levels of 4-AP showed a terminal half-life of approximately  $3 \pm 1$  hours. There was no detectable serum 4-AP in the majority of patients on the morning following the test day, although 7/17 patients had varying carryover levels. These carryover levels were lower than any from the previous day and clinical improvements had reversed to baseline by this time.

Side effects of this dosage (which is three times higher than we propose) seen were mild to moderate consistently

lasted no more than 60-90 minutes. These were generally well tolerated and patients did not consider them disturbing.

**4. Orally administered 4-aminopyridine improves clinical signs in multiple sclerosis.** Davis FA, Stefoski D, Rush J. Ann Neurol. 1990 Feb;27(2):186-92.

In these studies, 4 AP was delivered orally in a single dose and no serious or bothersome side effects were observed with single oral doses of up to 25 mg. These dosages were up to 2 times greater than any used in this proposal.

**5. The effects of 4-aminopyridine in multiple sclerosis patients: results of a randomized, placebo-controlled, double-blind, concentration-controlled, crossover trial.** Bever CT Jr, Young D, Anderson PA, Krumholz A, Conway K, Leslie J, Eddington N, Plaisance KI, Panitch HS, Dhib-Jalbut S, et al. Neurology. 1994 Jun;44(6):1054-9.

In patients given anywhere from 5-10 mg of 4-AP after various time points(i.e., q12h, q8h, q6h) serum levels only once exceeded 64 ng/ml in one patient and 56 ng/ml in one patient and otherwise were all between 35-51 ng/ml at the Cmax analysis point. The only time seizures were seen was in a patient where the serum level reached, with high dosage administration, greater than 100 ng/ml. The conclusion of this study was that peak serum levels above 100 ng/ml should be avoided but that at lower levels side effects are minimal.

The studies on multiple sclerosis define the dosages to be used in this proposal, even though the traumatically injured patients are not considered to be a fragile population. The following studies on patients with spinal cord injuries are also relevant, as these patients, like peripheral nerve injury patients, do not have the central nervous system lesions that are prominent in patients with multiple sclerosis.

**6. Safety and efficacy of 4-aminopyridine in humans with spinal cord injury: a long-term, controlled trial.** Segal JL, Pathak MS, Hernandez JP, Himber PL, Brunnemann SR, Charter RS. Pharmacotherapy. 1999 Jun;19(6):713-23.

In these patients with chronic spinal cord injuries, dosages provided in immediate release oral formulations of 4-AP were 30 mg per day and demonstrated efficacy in multiple patients. Clinically significant adverse effects or measurable toxicity did not occur. Nervousness, giddiness or dizziness, and gastrointestinal upsets manifesting as mild abdominal cramping or nausea were the most frequent side effects. Side effects were transient, self-limiting and seizures or seizure-like activity was not observed.

The authors stated that they have administered an oral formulation in amounts of up to 40 mg/day to more than 60 patients with no significant toxicities or adverse reactions that warranted discontinuing a subject. This is generally the case, and patients with spinal cord injury have been studied at dosages higher than those used in patients with multiple sclerosis.

**7. Effect of 4-aminopyridine on gait in ambulatory spinal cord injuries: a double-blind, placebo-controlled, crossover trial.** DeForge, D., Nymark, J., Lemaire, E., Gardner, S., Hunt, M., Martel, L., Curran, D., Barbeau, H., 2004.. Spinal cord 42, 674-685.

15 chronic, ambulatory SCI patients were randomized to an initial 2 weeks of 40mg/day, oral medication of either placebo or immediate-release 4-AP and subsequently crossed over to the alternate medication for the following 2 weeks. The study treatment (placebo or 4-AP) started at 5 mg twice daily for 3 days, increased to 10 mg twice daily for 3 days and finally 10 mg four times daily. The subjects were on the full dosage of 40 mg/day within 1 week. Side effects consisted of nausea, dizziness and sleeping difficulties but did not include seizures even though dosages were twice those studied in patients with multiple sclerosis.

8. Sustained improvements in neurological function in spinal cord injured patients treated with oral 4-aminopyridine: three cases. Potter, P.J., Hayes, K.C., Hsieh, J.T., Delaney, G.A., Segal, J.L., 1998.. Spinal cord 36, 147-155.

Potter and colleagues examined three patients with SCI who were administered oral (capsule) IR-4AP (10 mg b.i.d. or t.i.d.) over a 4 month interval. Only trivial side effects (transient light-headedness) were observed.

## **2.3 Study Rationale**

More research is needed to evaluate the role of 4-aminopyridine (4AP) in the course of assessment of nerve continuity after peripheral nerve traction and/crush injuries. The investigational treatment will be used to test the hypothesis that 4AP allows the identification of incomplete injuries earlier than standard electrodiagnostic (EDX) and clinical assessment and may have a role in faster triage.

# **3.0 Inclusion and Exclusion Criteria**

## **3.1 Inclusion Criteria**

- Patients with trauma involving two or less limbs where the continuity of a given peripheral nerve or nerves is unclear on presenting physical examination.
- Closed soft tissue envelope obscuring direct observation of the continuity of the affected nerve.
- Cognitive ability to report sensory and motor deficit during examination.
- Able to complete single day dosing within seven days (168 hours) of nerve injury diagnosis.
- Eligible for standard of care plan of monitoring vs surgical exploration of the nerve.
- Adults subject aged 18-90
- Known limb trauma which resulted in nerve injury (aim 1) or post-operative/post intervention nerve injury (aim 2).
- Ability to give written informed consent.
- Capable of safely undergoing electrodiagnostic testing (EDX).
- Availability for all testing days and main trial day.

## **3.2 Exclusion Criteria**

- Not able to complete dosing within seven days (168 hours) of nerve injury diagnosis
- Distracting injury which prevents adequate examination.
- Plan for surgical exploration of the nerve during the ensuing 48 hours.
- Plan for surgical exploration of the nerve as part of another surgical procedure within 48 hours of evaluation.
- Intoxication during examination or evidence of cognitive deficit that emerges during examination.
- History of multiple sclerosis, stroke or any other diagnosed neurological disorder
- History of hypersensitivity to AMPYRA® or 4-aminopyridine
- Current use of aminopyridine medications, including other compounded 4-AP
- Renal impairment based on calculated GFR (GFR<80 mL/min). This laboratory value is measured in all inpatient trauma patients as part of the standard of care.
- History of difficult compliance with timely follow up or plan to seek care at another institution closer to home.
- Patients outside the age range or unable to consent.
- Patients with a known history of a seizure disorder (4AP overdose can, in selected cases, result in limited seizure activity).
- Patients with a concomitant traumatic brain injury.

- Patients unable to communicate return or loss of sensation.
- Patients unable to exhibit motor control on the affected limb at baseline.
- Patients unwilling to complete the study requirements.
- Patients with injuries too extensive to isolate a single nerve(s) for testing.
- Patients currently taking organic cat-ion transporter 2 (OCT2) inhibitors, e.g. Cimetidine.
- Pregnancy, breastfeeding or incarcerated individuals.

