## **7.2 Study Procedures**

This is a pilot, single-center, inpatient Clinical Research Center study that will be conducted at Penn State Hershey. Subjects will be randomized to treatment or placebo for each aim. Both the subject and investigator will be blinded to group assignment for the duration of the trial.

**Study Participant Source:** Study participants will come from two sources. The first will be traumatized patients presenting with nerve dysfunction. These study participants are referred to as study participants for aim 1 of this trial. These patients often have concomitant orthopaedic injuries, which require stabilization. If the nerve was dysfunctional before intervention, then the patient will be included as a recruit for aim 1. The second source is patients who suffer nerve dysfunction after a surgery or intervention where nerve injury may not have been expected, as is the case with routine fracture fixation or joint arthroplasty procedures. In such cases, post-intervention examination may reveal a loss of nerve function where the continuity of the nerve again cannot be established. These patients, owing to their intact nerve function before the intervention, will be included as recruits to aim 2. In point of fact, both groups of patients have the same phenotypic condition, namely the loss of nerve function where the continuity of the nerve is not demonstrable. However, they are grouped into differing aims because the latter group suffers nerve dysfunction as the result of an intervention or surgical procedure and critically, these patients will have a clear pre-intervention examination without any nerve dysfunction.

Study participant **screening procedures** include the interview and chart review of patients to ensure that they match the inclusion and exclusion criteria listed in section 3.1 and 3.2. This will be performed on first interview with the patient on presentation for both Aim 1 and Aim 2 in the hospital (either inpatient ward or emergency department).

Potential study participants will be pre-screened for eligibility by reviewing the EMR to confirm inclusion and exclusion criteria. Study participants meeting pre-screening criteria will be presented with the study

opportunity. After obtaining informed consent, patients will be provided a research diary and instructed on its use.

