#### **8.0 Subject Numbers and Statistical Plan**

### **8.1 Number of Subjects**

This is a pilot study. The purpose is to gain preliminary data and refine infrastructure and establish finalized routines associated with our work. We hope to recruit 50 patients to this pilot study based on our previous statistical analysis.

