Estimated glomerular filtration rate (GFR) is assessed in trauma patients and will be known before initiating treatment with 4-AP. The relationship between 4AP dosage and estimated GFR levels is based on the importance of renal function in removing 4AP from the system. In patients with mild renal impairment (estimated GFR 51–80 mL/min), 4-AP plasma levels may approach those seen at a dose of 15 mg twice daily, a dose that may be associated with an increased risk of seizures. As mild renal impairment is common after age 50, estimating GFR is particularly important in such patients. Patients with renal impairment (estimated GFR≤80 mL/min) will be excluded from the study based on the fact that this level of impairment is contraindicated

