### **Protection Against Risks**

Breaches of confidentiality will be reduced by storing the data on secure share drives within Penn States Trial Data Center (part of the Department of Public Health Sciences). Access will be restricted to the investigators, the study coordinator, and any agency legally empowered to demand access to the data and only encrypted, password-protected computers will be used.

Potential risks and discomforts from taking the study medication will be minimized to the greatest extent possible by closely monitoring subjects for the most common side effects including allergic reactions and the less common side effect of seizure while in the CRC and after discharge (see above). Study subjects will be asked by study personnel after the CRC day about any potential symptoms and any evidence of difficulty or adverse event will be evaluated.

Estimated glomerular filtration rate (GFR) is assessed prior to inclusion in this study and in trauma patients as standard of care and will be known before initiating the trial with 4-AP. In patients with mild renal impairment (estimated GFR 51-80 mL/min), 4-AP plasma levels may approach those seen at a dose of 15 mg twice daily, a dose that may be associated with an increased risk of seizures. As mild renal impairment is common after age 50, estimating GFR is particularly important in these subjects. Patients with renal impairment (estimated GFR≤80 mL/min) will be excluded from the study based on the fact that this level of impairment is contraindicated in the use of 4-AP.

4-AP has never been shown to definitively exacerbate renal function in humans and studies in animals only reveal alterations at doses several-fold higher than are used in our proposed study. The relationship between 4AP dosage and

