estimated GFR levels is based on the importance of renal function in removing 4-AP from the system. Therefore, the risk of 4-AP use in this patient population is directly linked to the risk of changes in estimated GFR. To be on the safe side of renal clearance issues, however, we have taken two specific steps with regards to issues with 4-AP in renal toxicity. First, we have excluded patients with estimated GFR  $\leq 80$  mL/min based on the fact that this level of impairment is contraindicated in the use of the study drug. This criteria means that we even have excluded patients whose estimated GFR levels actually met criteria for inclusion in earlier 4-AP trials. Second, we are using lower doses of 4-AP in this study than were used in initial studies for 4-AP for a variety of neurological maladies to further ensure we do not run into toxicity issues. The specific dose we have selected is the starting dose used in multiple sclerosis patients prior to dose escalation.

Randomization errors are protected against in this trial by double checking the randomization protocol in IDS and use of redcap. Further checking and oversight is planned at the DSMB level prior to initiating the trial and after the 80% mark is achieved.

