#### **18.7 Stopping Rules**

Our safety analysis plan includes routine review (urgently within 48 hours) of every adverse event to the data safety monitoring board. The board will render a decision on suspension of the trial based on the available data in an unbiased manner. Examples of reasons for such a stoppage include adverse events that are not explainable, and patient dissatisfaction with the trial progression. The rules for stopping are not confined to adverse events, as defined by the drug information insert. The data safety monitoring board has the power to stop the trial for any reason surrounding safety, even if that includes investigating a particular patient's response to the trial drug or evaluation of the circulating levels of the drug at the time of an adverse event. Stopping rules include: Seizure, increased pain not treatable in the clinical research center, clear demonstration of a positive result which alters the statistical numbers for the trial, clear indications of deviations from the protocol, inadequate reporting by the trial team, and incomplete documentation of results.

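### The screening list in section 3.2 excludes GFR below 80 mL/min, but sections 9.1 and 10.0 exclude 80 and below, so a patient at exactly 80 passes screening against the protocol's own safety rule

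*Combined protocol and SAP*

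**What the plan says.** Section 3.2 lists as an exclusion "Renal impairment based on calculated GFR (GFR<80 mL/min". Section 7.2 makes that list operative: patients are interviewed and their charts reviewed "to ensure that they match the inclusion and exclusion criteria listed in section 3.1 and 3.2". Section 4.2.4 adds that eligibility questioning does not go beyond verifying those criteria.

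The safety sections set a different limit. Section 9.1 states: "Patients with renal impairment (estimated GFR≤80 mL/min) will be excluded from the study". Section 10.0, under Protection Against Risks, repeats the limit of 80 or less. It gives as the reason that "this level of impairment is contraindicated in the use of 4-AP", and then presents the same exclusion as the first of two specific steps taken for renal safety. Both sections also define the range of concern. In the words of section 10.0, in "mild renal impairment (estimated GFR 51-80 mL/min), 4-AP plasma levels may approach those seen at a dose of 15 mg twice daily", a dose that the text links to a possibly increased seizure risk.

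Section 18.7 shows why the limit is there: "Stopping rules include: Seizure, increased pain not treatable in the clinical research center".

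On timing, sections 3.1 and 3.2 both require dosing within 168 hours of the diagnosis of nerve injury. Section 15.2 describes eligible patients as within 7 days of injury, and the EDX testing text in section 7.2 places early testing within four days of injury.

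**The concern.** An eligibility limit should read the same wherever it appears, above all when it is a safety limit. Here the looser version is in the list that staff apply, and the stricter one is in the sections that explain the risk. No later step in the documents is described as applying the stricter limit before dosing.

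The mismatch runs in the unsafe direction. The protocol's reasoning is that reduced clearance raises 4-AP levels and that higher levels may bring seizures. A value of 80 falls inside the band that it names. Enrolment runs to age 90, and section 9.1 says that mild impairment is common after age 50, so values near the limit are foreseeable. At stake are the enrolment of a patient whom the protocol itself regards as contraindicated, and an eligibility record that an auditor could call both compliant and non-compliant.

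**Working it through.** The plan gives no figure to reproduce. The check compares the texts and then counts patients under stated assumptions.

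**Step 1: where the rules differ.** Illustrative GFR values in mL/min:

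- 79: excluded by 3.2, excluded by 9.1 and 10.0. They agree.
- 80: admitted by 3.2, excluded by 9.1 and 10.0. They conflict.
- 81: admitted by 3.2, admitted by 9.1 and 10.0. They agree.

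The conflict is confined to the single value 80.

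**Step 2: which rule was intended.** The limit of 80 or less appears once in section 9.1 and twice in section 10.0. The second time in section 10.0 it is again justified because "this level of impairment is contraindicated in the use of the study drug". The 51-80 band ends at 80 inclusive. The strict inequality appears only in 3.2, so 3.2 is the outlier.

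**Step 3: expected number of patients at exactly 80.**

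- N = 50, from section 8.1: "We hope to recruit 50 patients to this pilot study".
- p = share of subjects reported at exactly 80. The documents do not give it; 0.5%, 1% and 2% are assumed.
- Expected number = N × p: 50 × 0.005 = 0.25; 50 × 0.01 = 0.5; 50 × 0.02 = 1.0.
- On active drug, if allocation is 1:1 (the ratio is not stated): 0.25 / 2 = 0.125; 0.5 / 2 = 0.25; 1.0 / 2 = 0.5.
- Section 3.3.2 allows 25 to 34 subjects per aim. At the upper end N = 2 × 34 = 68, and with p = 2% the expected number is 68 × 0.02 = 1.36, or 1.36 / 2 = 0.68 on active drug. The order of magnitude does not change.

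**Step 4: the time anchor.** If diagnosis comes d days after injury, sections 3.1 and 3.2 allow dosing up to day d + 7 after injury. For assumed d = 0, 1, 2 and 3 this is day 7, 8, 9 and 10. Section 15.2, read as a limit, stops at day 7. The documents give no figure for d. Section 4.1 describes identification in the emergency department or during inpatient consultation, which suggests that d is usually small.

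**The case against.** The strongest reply is that the protocol, read as a whole, already excludes the patient at 80: it states the stricter limit three times, and section 10.0 says GFR is assessed before inclusion. Section 19.1.2 also has an ethicist review every proposed consenting patient. That settles the intent but not the practice. Section 7.2 sends screeners to 3.1 and 3.2, and the ethicist's review is not described as a check of renal function. The point does turn on one character in 3.2, so the sign should be confirmed in the approved protocol.

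A reader might infer that the mismatch creates a material seizure hazard. The documents do not support that. The comparison in sections 9.1 and 10.0 is with a 15 mg twice-daily regimen, whereas sections 7.1 and 7.4 provide for one 10 mg dose under observation. Section 2.2 reports no serious or bothersome effects with single oral doses up to 25 mg, although in multiple sclerosis patients under the heading of immediate-release studies. Some of the few patients concerned would also receive placebo. This objection stands, and it is why the point is minor.

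A reader might also infer that the timing statements are a second eligibility defect, or that late testing undermines the EDX comparison. The two operative criteria agree with each other, and the differing statements are a parenthesis in a feasibility section and a remark in the EDX text. The EDX text expects most trial-day studies, not all, to be inconclusive, and provides for a conclusive result. Each patient has a baseline EDX before dosing, and the comparison is with randomised placebo within each aim. No harm to inference is shown, so timing is an optional clarification.

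**Conclusion.** The GFR conflict is real and certain on the text: at exactly 80 mL/min the screening list admits a patient whom sections 9.1 and 10.0 exclude as contraindicated. It deserves correction because it concerns the main renal safeguard and errs toward exposure. Its weight is minor. About one of 50 patients at most is affected, on assumed shares of 0.5% to 2% for which the documents give no data, and about half as many receive drug if allocation is 1:1. It changes no estimate, error rate, power or sample size.

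**What to change.** Change the renal criterion in section 3.2 to exclude GFR ≤80 mL/min, matching sections 9.1 and 10.0, and update the screening form. The cost is one wording amendment, and patients at exactly 80 become ineligible.

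Optional, in the same amendment: keep diagnosis as the anchor for the 168-hour window, align section 15.2 and the four-day remark in the EDX text of section 7.2 with it, and record the injury-to-dosing interval for each patient. This loses no patients and adds one data item. Moving the anchor to injury is not recommended: it would exclude some late-diagnosed patients from a limited pool (section 15.2 puts aim 1 presentations at no fewer than 24 a year) for a benefit that has not been quantified.
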